1.2 Product Development Rationale

In 2009, an estimated 27,360 men in the United States died from advanced metastatic prostate cancer, making prostate cancer the second most lethal malignancy among US men.¹ Also, an estimated 192,280 men were diagnosed with prostate cancer, and around 7,700 of those men had incurable disease (i.e., metastatic) at diagnosis.¹ Androgen suppression therapy (AST) is the most effective systemic therapy for these patients with incurable prostate cancer. Currently, the most promising approach to extending survival and protecting quality of life in these men is to identify ways to enhance the depth and duration of response to AST.

In a 2006 publication, Hussain, et al., examined outcomes in 1,345 such patients.² As shown below, the PSA nadir maintained after 6 to 7 months of AST was a powerful predictor of overall survival. Those patients who achieved an undetectable PSA fared best. The definition of undetectable PSA in this paper was a PSA \leq 0.2.

PSA (ng/mL)	Number of Patients	Median Survival (months)
>4	383	13 (95% CI, 11-16)
≤4, >0.2	360	44 (95% CI, 39-55)
≤0.2	602	75 (95% CI, 62-91)

Hussain and colleagues were able to discriminate between men at high and low risk of dying from castration resistant prostate cancer (CRPC) at a point in the disease process when the disease burden is minimal. This discovery creates a novel opportunity to target this minimal volume androgen-independent disease early with the hope of altering the grim natural history of this disease state. Hussain's data also demonstrate that a complete PSA response to initial therapy is likely a pre-requisite for long-term survival.

[figure not shown]
An emerging class of agents that target immune functions has shown promise in treating advanced prostate cancer. It is believed that cancer cells can evade immune detection by

[figure not shown]

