Treatment with ipilimumab resulted in clinical activity in pretreated and previously untreated subjects with advanced melanoma. Clinically relevant reductions in the tumor burden from baseline were reported, together with a preliminary evidence of improved overall survival compared with published survival rates. These findings, together with evidence of a safety profile that is manageable with careful monitoring and appropriate intervention for treatment of immune-related toxicities, suggest an acceptable benefit to risk ratio.

Men with metastatic prostate cancer who do not obtain and maintain a complete biochemical response (PSA \leq 0.2 ng/ml) to AST alone have a very poor prognosis.² The median survival of this study population is only 13 to 44 months, where a PSA > 4.0 ng/ml after induction AST has the shortest median survival. Chemotherapy using docetaxel with prednisone is currently an option for men with CRPC. While there have been no direct comparisons of toxicity between ipilimumab and docetaxel, we anticipate that the overall toxicity of chemotherapy is greater. Since the initial approval of this study, several other agents have gained approval in CRPC, namely abiraterone with

prednisone, enzalutamide and sipuleucel-T. Although they have been shown to improve overall survival, their benefit compared to placebo is on the order of 2-4 months, and there is still a clear need to improve survival in this group. Furthermore treatment with ipilimumab does not disqualify patients from being treated with these other agents.

The early identification of this aggressive subset of metastatic prostate cancer offers significant opportunities for benefit in the form of delayed progression and longer survival with successful intervention. The overall risk-benefit ratio for patients entering this protocol is therefore at least comparable to and possibly better than alternative options.

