8.3 Sample Size Justification

N=30 (for the final analysis, 10 for the intial analysis). Using the Simon two-stage design for Phase II trials, the initial accrual will be 10 patients. Assuming that 10% of patients receiving usual care will achieve an undetectable PSA (PSA \leq 0.2) without additional intervention, the trial has a 80% power to detect a rate of achieving an undetectable PSA of \geq 30% among patients treated with ipilimumab. At least two patients with an undetectable PSA will be required in the first 10 patients to continue to stage 2. As soon as two patients having achieved an undectable PSA are identified, stage 2 for of the study will begin. If 6 or more of 30 patients have achieved an undetectable PSA at 6 months, the study will be considered successful and the regimen worthy of further investigation. This design has a type I error rate of 0.05 and a type II error rate of 0.20.

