8.5 Statistical Analysis Plan

Demographic and clinical characteristics will be summarized using descriptive statistics (e.g. proportions, mean, standard deviation, median, range). The proportion of patients who achieve an undetectable PSA (≤ 0.2 ng/ml) after initiation of ipilimumab therapy will be provided with the exact 95% confidence interval. The Kaplan-Meier method will be used to estimate time to PSA progression, time to disease progression by any measure and time to death from any cause. In evaluation of time to PSA progression and time to disease progression by any measure will be censored for:

- 1) lost to follow-up at the date of last contact
- 2) use of additional cancer therapies that would interfere with ascertainment of the endpoint of interest
- death from a causes other than prostate cancer or treatment of prostate cancer.

Evaluation of time to death will be censored for lost to follow-up at last contact.

The effects of IRAEs and other immune parameters (e.g., a ratio of T regulatory cells to T effector cells) on clinical outcomes will be evaluated using logistic regression for binary endpoints (e.g., achievement of undetectable PSA) and Cox regression for the time to event outcomes (e.g., time to PSA progression).

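### Section 8.5 uses entry PSA as neither a stratum nor a covariate, although the protocol's own table links post-AST PSA to a 13- versus 44-month median survival among eligible men

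*Combined protocol and SAP*

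**What the plan says.** Section 1.2 reports that "the PSA nadir maintained after 6 to 7 months of AST was a powerful predictor of overall survival" and tabulates median survival by that value:

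- PSA above 4 ng/ml: 13 months (95% CI 11 to 16), 383 men
- PSA above 0.2 up to 4: 44 months (39 to 55), 360 men
- PSA 0.2 or below: 75 months (62 to 91), 602 men

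Section 1.4 carries the first two rows over to this trial: "The median survival of this study population is only 13 to 44 months". Section 4.1 admits men with PSA above 0.2 after 6 to 18 months of AST and sets no upper limit, so both rows are eligible. The hypothesis in Section 1.1 is that outcomes will come to resemble those of men with a complete biochemical response.

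Section 8.5 plans Kaplan-Meier estimates of time to PSA progression, time to any progression and time to death, with no strata named. The effects of IRAEs and immune parameters on outcomes "will be evaluated using logistic regression for binary endpoints (e.g., achievement of undetectable PSA) and Cox regression for the time to event outcomes", with no covariates named.

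Entry PSA does appear elsewhere. Under Section 6.4.2.1 it is the denominator of maximum PSA reduction, and baseline PSA is one reference value for PSA progression. The Time and Events Schedule (Section 6.1) has PSA drawn at screening and week 1.

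**The concern.** The protocol's strongest stated prognostic factor plays no prognostic role in the analysis. This has two consequences.

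First, the survival to be expected without any benefit depends heavily on how many enrolled men have PSA above 4. A single pooled median does not reveal that mix, so the same observed value could look encouraging or discouraging according to who was recruited.

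Second, the IRAE and immune-parameter Cox models compare men who were not randomised to those exposures. If men with and without an IRAE differ in entry PSA, part or all of an apparent association could reflect PSA. Thirty men leave ample room for this by chance. There may also be a systematic route: men who progress receive no maintenance doses (Sections 3.5 and 5), so men with a worse prognosis may have less exposure in which to develop an IRAE.

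**Working it through.** **The plan's own figure.** Section 8.3 gives a null rate of 10%, an alternative of 30%, at least 2 of 10 to continue and at least 6 of 30 for success. The exact two-stage calculation is

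P(success) = Σ over x from 2 to 10 of P(X1 = x | 10, p) × P(X2 ≥ 6 − x | 20, p).

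At p = 0.30 this is 0.815, which agrees with the stated 80% power. At p = 0.10 it is 0.0525, marginally above the stated 0.05. Nothing below depends on either value.

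**No-benefit median survival by PSA mix.** Inputs are the medians 13 and 44 months (Section 1.2) and w, the share of enrolled men with PSA above 4. The documents do not give w for this trial, so 20% to 80% is assumed; the table's own counts give 383/(383 + 360) = 383/743 = 51.5%. Exponential survival within each group is also assumed. Solve

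w × 0.5^(t/13) + (1 − w) × 0.5^(t/44) = 0.5.

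| Share with PSA > 4 | Median (months) |
|---|---|
| 20% | 34.1 |
| 40% | 25.9 |
| 51.5% | 22.2 |
| 60% | 19.9 |
| 80% | 15.8 |

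Check at 20%: 0.2 × 0.162 + 0.8 × 0.584 = 0.50.

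If the true share were 51.5%, the 95% binomial range in 30 men is 10 to 21 with PSA above 4, and the median moves from 28.4 to 17.7 months by chance alone. With both medians at the ends of their confidence intervals (11 and 39, or 16 and 55), the 51.5% figure runs from 19.1 to 27.4 months. An observed median of 26 months would therefore match a no-benefit population at a 40% share, exceed it by about 10 months at 80% (26 − 15.8), and fall short by about 8 at 20% (34.1 − 26).

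**Imbalance in the Cox models.** Under exponential survival the hazard ratio between the two PSA groups is 44/13 = 3.4. In a large simulated sample (20,000 men, censored at 60 months), a marker with no true effect on survival gave these unadjusted hazard ratios:

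- 0.81 when 40% of marker-positive and 60% of marker-negative men have PSA above 4
- 0.66 at 30% and 70%
- 0.50 at 20% and 80%

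**Room for one covariate.** Expected deaths by 60 months are 30 × [1 − S(60)], where S is the left-hand side of the equation above. This gives 20.4, 23.7 and 26.7 at shares of 20%, 51.5% and 80%: enough for one prespecified covariate, not for many.

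**Power.** Assume a true IRAE hazard ratio of 0.50, IRAE prevalence of 70.4% (the 10 mg/kg melanoma arm in Table 1) and censoring uniform over 36 to 90 months. Power with 30 men is then about 23–25% without PSA in the model and 28–30% with it.

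**The case against.** Several objections have force.

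- **A reader might infer that entry PSA is not analysed at all.** The documents contradict this: Section 6.4.2.1 uses it in two secondary endpoints. What is missing is its use as a stratum or covariate.
- **A reader might infer that survival can never be compared with the historical figures.** Section 8.5 plans no such comparison; the 13-to-44-month range sits in the risk/benefit rationale. Because PSA is collected, a mix-weighted reference could be computed later. It is simply not prespecified.
- **That the models are unadjusted is read from silence.** Section 8.5 is brief, names no covariates, and does not say the models are univariable.
- **Setting each PSA group against its own table row would be unsound.** The table classifies men by nadir maintained after 6 to 7 months of AST, whereas entry PSA is a single value after 6 to 18 months. A man entering at month 18 has already survived 11 to 12 months past the table's classification point. Entry also requires ECOG 1 or below and life expectancy of at least 6 months. Such a comparison may favour treatment, and the documents do not give the cited study's time origin or eligibility. For the same reason, 3.4 is only a guide to the effect of entry PSA.
- **Omitting a balanced covariate does little harm here.** A conditional hazard ratio of 0.50 becomes about 0.56 when PSA is left out. That is non-collapsibility, not confounding; it vanishes when there is no effect, and the shift of about 0.12 on the log scale is roughly a quarter of the standard error of 0.46 to 0.48 at n = 30. The case for adjustment rests on imbalance, not on this shift.
- **Subgroups will be small.** Three responders among 15 men give an exact 95% interval of 4% to 48%.

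All of these stand. They limit the claim and rule out a row-by-row comparison, but none justifies leaving the role of entry PSA unspecified.

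**Conclusion.** The point holds as a low-cost improvement to the secondary and exploratory analyses. By the protocol's own account, post-AST PSA separates eligible men into groups with median survival of 13 and 44 months, and Section 8.5 gives it no prognostic role. The pooled no-benefit median could lie anywhere from about 34 to 16 months, given exponential survival, an assumed 20% to 80% share with PSA above 4, and entry PSA as a proxy for the tabulated nadir. PSA imbalances of 20 to 60 percentage points could produce hazard ratios of 0.81 to 0.50 for a marker with no effect; these are illustrations, since the actual imbalance is unknown.

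The primary proportion, its exact interval and the 6-of-30 decision rule are not called into question. Adjustment will not make the IRAE analysis well powered; its value is protection against imbalance and easier interpretation.

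**What to change.** In Section 8.5:

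1. Name log entry PSA as the one prespecified covariate in the Cox models for IRAEs and immune parameters, label those models exploratory, and state which pre-treatment value counts as entry PSA.
2. Report the primary proportion, progression and survival descriptively by entry PSA (above 0.2 up to 4; above 4 ng/ml), with confidence intervals and no test between groups. Fixing the cut-off now avoids a data-driven choice.
3. If survival is set against the historical table, use a reference weighted to the enrolled PSA mix. State that it is only indicative, because of the different PSA measure, its timing, and the selection on ECOG and life expectancy.

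Leave the 6-of-30 rule unchanged. The cost is a few lines of text, one degree of freedom in each Cox model and wide subgroup intervals. No new data are needed.

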8.6 Safety Analysis

All toxicity and safety data including immune related Adverse Events (IRAEs) will be tabulated for each treatment group and summarized according to major organ categories of the NCI CTCAE v 4.0.

8.7 Efficacy Analysis

See section 9.5

9 ADMINISTRATIVE SECTION

9.1 Compliance with the Protocol and Protocol Revisions

The protocol and informed consent form for this study must be reviewed and approved in writing by the OHSU Knight Cancer Institute Clinical Research Review Committee (CRRC) and Institutional Review Board (IRB) at OHSU prior to any patient being registered on this study at OHSU. In addition, the protocol and informed consent must be reviewed by the IRB of each institution participating in this Prostate Cancer Clinical Trials Consortium (PCCTC) study before any patients may be registered from those individual institutions.

Any modification of this protocol must be documented in the form of a protocol revision or amendment signed by the principal investigator and approved by the OHSU CRRC and OHSU IRB, before the revision or amendment may be implemented. The only circumstance in which the amendment may be initiated without regulatory approval is for a change necessary to eliminate an apparent and immediate hazard to the patient. In that event, the investigator must notify the CRRC and IRB in writing within 10 working days after the implementation. Investigators holding the IND must notify FDA of substantive changes to the protocol.

9.2 Informed Consent

Investigators must ensure that subjects, or, in those situations where consent cannot be given by subjects, their legally acceptable representative, are clearly and fully informed about the purpose, potential risks, and other critical issues regarding clinical studies in which they volunteer to participate. Freely given written informed consent must be obtained from every subject or, in those situations where consent cannot be given by subjects, their legally acceptable representative, prior to clinical study participation, including informed consent for any screening procedures conducted to establish subject eligibility for the study.

The rights, safety, and well-being of the study subjects are the most important considerations and should prevail over interests of science and society.

9.3 Records and Reports

If the investigator relocates or for any reason withdraws from the study, the study records must be transferred to an agreed upon designee, such as another institution, another investigator, or to the OHSU Knight Cancer Institute Clinical Research Management. Records must be maintained according to sponsor or FDA requirements.

9.4 Good Clinical Practice

This study will be conducted in accordance with Good Clinical Practice (GCP), as defined by the International Conference on Harmonisation (ICH) and in accordance with the ethical principles underlying European Union Directive 2001/20/EC and the United States Code of Federal Regulations, Title 21, Part 50 (21CFR50).

The study will be conducted in compliance with the protocol. The protocol and any amendments and the subject informed consent will receive Institutional Review Board/Independent Ethics Committee (IRB/IEC) approval/favorable opinion prior to initiation of the study.

All potential serious breaches must be reported to BMS immediately. A serious breach is a breach of the conditions and principles of GCP in connection with the study or the protocol, which is likely to affect, to a significant degree, the safety or physical or mental integrity of the subjects of the study or the scientific value of the study.

Study personnel involved in conducting this study will be qualified by education, training, and experience to perform their respective task(s). This study will not use the services of study personnel where sanctions have been invoked or where there has been scientific misconduct or fraud (e.g., loss of medical licensure, debarment).

Systems with procedures that ensure the quality of every aspect of the study will be implemented.

9.5 Institutional Review Board/Independent Ethics Committee (IRB/IEC)

Before study initiation, the investigator must have written and dated approval/favorable opinion from the IRB/IEC for the protocol, consent form, subject recruitment materials/process (e.g., advertisements), and any other written information to be provided to subjects. The investigator should also provide the IRB/IEC with a copy of the

Investigator Brochure or product labeling, information to be provided to subjects and any updates.

The investigator should provide the IRB/IEC with reports, updates and other information (eg, expedited safety reports, amendments, and administrative letters) according to regulatory requirements or institution procedures

9.6 Records Retention

The Investigator must retain Ipilimumab disposition records, source documents, and case histories designed to record all observations and other data pertinent to the investigation (e.g. case report form) for the maximum period required by applicable regulations and guidelines, or Institution procedures.

If the Investigator withdraws from the study (e.g., relocation, retirement), the records shall be transferred to a mutually agreed upon designee (e.g., another Investigator, IRB). Documentation of such transfer must be provided to BMS.

APPENDIX 1 LIST OF ABBREVIATIONS

Abbreviation Term

ANC Absolute Neutrophil Count
AST Androgen Suppression Therapy

BID Twice a Day

BMS Bristol-Myers Squibb Company
CT scan Computed Axial Tomography scan

CBC Complete Blood Count
CR Complete Response
DLT Dose Limiting Toxicity

DSMB Data Safety Monitoring Board

ECOG PS Eastern Cooperative Oncology Group Performance Status
HIPAA Health Insurance Portability and Accountability Act

IRB Institutional Review Board

irRC Immune related response criteria
MRI Magnetic Resonance Imaging
PCWG2 Prostate Cancer Working Group 2

PD Progressive Disease

PFS Progression Free Survival

PO By Mouth

PR Partial Response
QD Once Daily
QoL Quality Of Life

RECIST Response Evaluation Criteria In Solid Tumors

SAE Serious Adverse Event

[figure not shown]
SPD Sum of the products diameters

SD Stable Disease

TNM Staging Tumor, Node and Metastasis Staging

TA Tumor assessment

APPENDIX 2 GENERAL RECOMMENDATIONS FOR IMMUNE-RELATED ADVERSE EVENTS (IRAES)

^{**} Based on clinical experience to date, systemic steroids for treatment of irAEs do not appear to impact the development or maintenance of ipilimumab clinical activity in advanced melanoma.

APPENDIX 3 SUGGESTED WORK-UP AND TREATMENT FOR IMMUNE-RELATED ADVERSE EVENTS (IRAES)

An IRAE is defined as an adverse event of unknown etiology, associated with drug exposure and is consistent with an immune phenomenon. Efforts should be made to rule out neoplastic, infectious, metabolic, toxin or other etiologic causes prior to labeling an adverse event a non-dermatologic, immune-mediated event. Serological, immunological, and histological (biopsy) data should be used to support the diagnosis of an immune-mediated toxicity. Documentation of test results should be included in the patient's medical record.

Gastrointestinal (diarrhea) and skin (rash)-related toxicities have been the most common IRAEs noted in prior studies with ipilimumab. Suggested work-up procedures for suspected IRAEs of the gastrointestinal tract, liver, skin, eye, pituitary, and adrenal gland are listed below. When symptomatic therapy is inadequate or inappropriate, an IRAE should be treated with steroids followed by a slow taper.

Gastrointestinal Tract: Diarrhea (defined as either first watery stool, or increase in frequency 50% above baseline with urgency or nocturnal bowel movement, or bloody stool) should be further evaluated and infectious or alternate etiologies ruled out. Patients should be advised to inform the investigator if any diarrhea occurs, even if it is mild. An algorithm for working up patients with diarrhea or suspected colitis is provided in Appendix 4.

If the event is of significant duration or magnitude or is associated with signs of systemic inflammation or acute phase reactants (e.g., increased CRP or platelet count; or bandemia), it is recommended that sigmoidoscopy (or colonoscopy, if appropriate) with colonic biopsy with 3 to 5 specimens for standard paraffin block be performed. If possible, 1 to 2 biopsy specimens should be snap frozen and stored. All patients with confirmed colitis should also have an opthomological examination, including a slit-lamp exam, to rule out uveitis. Tests should also be performed for WBCs and for stool calprotectin.

Patients with colitis should discontinue any non-steroidal anti-inflammatory medications or any other medications known to exacerbate colitis symptoms. Investigators should use their clinical judgment as to whether corticosteroids are necessary to treat colitis associated with ipilimumab therapy and as to what dose should be used. As guidance prior experience suggests that colitis manifested as \geq Grade 3 diarrhea requires

corticosteroid treatment. For severe symptoms, prednisone 60 mg or equivalent may be required to control initial symptoms and the dose should be gradually tapered over at least one month in duration. Lower doses of prednisone may be considered for less severe cases of colitis. It is suggested that prednisone (for oral administration) or solumedrol (for intravenous administration) be corticosteroid of choice in the treatment of colitis.

Liver: Elevation of LFTs ≥ 3 fold from baseline should instigate an investigation into the underlying etiology for suspected IRAEs. Neoplastic, concurrent medications, viral hepatitis, and toxic etiologies should be considered and addressed, as appropriate. Imaging of the liver, gall bladder, and bile duct should be performed to rule out neoplastic or other causes for the increased LFTs. An ANA, pANCA, and anti-smooth muscle antibody test should be performed if an autoimmune etiology is considered. Consultation with a hepatologist is appropriate for a suspected liver IRAE and a biopsy should be considered.

Patients presenting with right upper-quadrant abdominal pain and/or unexplained nausea or vomiting should have LFTs performed immediately and reviewed before administering the next dose of study drug. Treating physicians should discuss, with the CRO Medical Monitor, unexplained increases in LFTs ≥ 3 fold from baseline prior to any additional study drug administration.

Pancreas: Symptoms of abdominal pain associated with elevations of amylase and lipase, suggestive of pancreatitis, may rarely be associated with anti-CTLA-4 monoclonal antibody administration. The differential diagnosis of acute abdominal pain should include pancreatitis. Appropriate workup should include serum amylase and lipase tests.

Skin: A dermatologist should evaluate persistent and/or severe rash or pruritus. A biopsy should be performed if appropriate and if possible, photos of the rash should also be obtained. Low-grade ipilimumab mediated rash and pruritus IRAEs have been treated with symptomatic therapy (e.g., antihistamines). Topical or parenteral corticosteroids may be required for more severe symptoms.

Eye: An ophthalmologist should evaluate visual complaints with examination of the conjunctiva, anterior and posterior chambers and retina; visual field testing and an electroretinogram should also be performed. Patients with ipilimumab related uveitis or episcleritis have been treated with topical corticosteroid eye drops.

Endocrine: Patients with unexplained symptoms such as fatigue, myalgias, impotence, mental status changes, or constipation should be investigated for the presence of thyroid, pituitary or adrenal endocrinopathies. An endocrinologist should be consulted if an endocrinopathy is suspected. TSH and free T4 levels should be obtained to determine if thyroid abnormalities are present. TSH, prolactin and a morning cortisol level will help to differentiate primary adrenal insufficiency from primary pituitary insufficiency. Appropriate hormone replacement therapy should be instituted if an endocrinopathy is documented.

Suspected IRAEs should be documented in the patient's medical record.

